# 6. TRIAL ENTRY

# Interventional Component

A treatment slot must be reserved for a cohort prior to providing potential patients with a Patient Information Sheet (PIS). This should be done by contacting the Trials Office. If a treatment slot is available and if consent is provided, a peripheral blood smear should be obtained in the first instance to assess whether patient is expected to fulfil the bone marrow blasts eligibility criterion and its result reported to the Trial Office in order to confirm the booked treatment slot. If the patient satisfies the remaining eligibility criteria, including bone marrow blasts ≥10%, the patient may be registered to the PHAZAR study.

Patients on the interventional component will be registered to the trial via the Cancer Research UK Clinical Trials Unit (CRCTU).

# **2**: [name]; 9am-5pm Monday to Friday.

# **Observational Component**

All patients who meet the entry criteria for the observational component may be registered to PHAZAR. Registration for the observational component will be conducted by logging on to:

# https://www.cancertrials.bham.ac.uk/PHAZARLive

Login details will be provided by the trials office as part of site initiation.

An eligibility checklist and registration form (found in the ISF) should be completed prior to registration by the Investigator or designee. The patient trial number and dose allocation (for those enrolled on the interventional component) will be given over the telephone, followed by a fax confirmation. The patient's trial number for patients on the observational component will be provided by the online system. A report can be printed as confirmation.

# 7. TREATMENT DETAILS

# 7.1 Trial Treatment – Interventional Component

Both 5-azacitidine and ruxolitinib are considered Investigational Medicinal Products (IMPs) for the purpose of the trial.

#### 5-azacitidine

Subcutaneous 5-azacitidine will be provided free of charge for the trial by Celgene for the duration of the study period. Patients will receive 5-azacitidine by subcutaneous (SC) injection on seven consecutive days (excluding weekends), starting day 1 of 28-day cycles, for up to 6 cycles. It is recommended that this is delivered in a 5-2-2 schedule. Cycles should commence on a Monday whenever possible. Every effort should be made to attend on the scheduled visit days, however if not possible administration visits may be arranged for +/- 3 days.

Patients who continue to gain a clinical benefit (in the opinion of the local investigator) will be permitted to continue with therapy beyond 6 cycles at the discretion of the CI.

5-azacitidine will be supplied as a lyophilised powder in 100 mg single-use vials. The IMPs will be packaged and labelled in accordance with local regulations and Good Manufacturing Practice (GMP), stating that the drug is for clinical trial use only and to keep it out of the reach of children. For further details on supply and labelling, refer to the pharmacy manual.

Method of 5-azacitidine administration: The 5-azacitidine should be reconstituted as per the SPC. Reconstituted 5-azacitidine should be injected subcutaneously into the upper arm, thigh or abdomen. Injection sites should be rotated. New injections should be given at least 2.5 cm from the previous site and never into areas where the site is tender, bruised, red, or hardened.

#### Ruxolitinib

Ruxolitinib will be provided free of charge for the trial by Novartis, in the form of 5 mg, 15 mg or 20 mg strength tablets. The allocated dose will be administered bd for up to 6 x 28-day cycles. Patients who continue to gain a clinical benefit (in the opinion of the local investigator) will be permitted to continue with therapy beyond 6 cycles at the discretion of the CI.

If patients are taking ruxolitinib at the point of study entry, they should continue to take the medication at their pre-study dose until the day prior to day 1 of cycle 1, at which point the dose will be changed to the appropriate study dose.

At the end of the patient's treatment, the dose of ruxolitinib should be tapered by 5 mg decrements to be completed over a 10-14 day period.

Medication labels will be in English. They will include storage conditions for the drug and the medication number but no information about the patient other than the trial number which will be added at the point of dispensing.

# 7.2 Trial Treatment – Observational Component

Patients on the observational component will not receive any trial treatment.

# 7.3 Treatment Schedule – Interventional Component

	Base	eline		Су	cle 1		c	ycle	2	Cycle 3		Cycle 4		Cycle 5		Cycle 6		e 6	Subsequent cycles		End of Study 			
Study schedule 	Within 28 days of registration	Within 7 days of registration	1	8	15	22	1	8	22	1	8	22	1	8	22	1	8	22	1	8	22	1	22	28 days after last treatment
Informed consent	х																							
Medical history & demographics	x																							
Physical examination and vital signs		x				x 			x 			x 			x 			x 			x 		x 	x
ECG		х	x	x	x	x		<pre><< as clinically indicated >></pre>																
Pregnancy test 		х																						
Haematology and biochemistry		x	x	x	x	x 	x	x	x 	x	x	x 	x	x	x 	x	x	x 	x	x	x 	x	x 	x
Peripheral blood smear (blast assessment)	x					x 			x 			x 			x 			x 			x²		x 	
Bone marrow inc. cytogenetics	x 											x 									x 		x 	
Disease assessment												x									x		x 	
Bone marrow for biobanking	x 											x 									x 			
Blood Samples for biobanking	x 											x 									x 			
Nail clippings and/or saliva collection for germline DNA	x																							
Transfusion assessment		x										Thr	ough	out S	Study									

	Base	eline		Сус	cle 1		С	ycle	2		Cycle	93	С	ycle	4	C	Cycle	5		Cycl	e 6	Subse cyc	equent cles	End of Study 
Study schedule 	Within 28 days of registration	Within 7 days of registration	1	8	15	22	1	8	22	1	8	22	1	8	22	1	8	22	1	8	22	1	22	28 days after last treatment
Quality of life assessment			x				х						х						х					
Adverse event reporting							-					Thr	ough	out s	study									x
Concomitant Medication		x		Throughout study																				
Ruxolitinib				Daily Daily throughout study  x 																				
5-Azacitidine				6 cycles in 5-2-2 schedule x 																				

1. Every effort should be made for patients to attend on the scheduled visit days. However, if a patient is unable to attend on the specified day, assessments may be scheduled for +/- 3 days.

2. The physical examination and peripheral blood smear may be performed from day 22 of the preceding cycle to the start of the next cycle at local discretion

- 3. Women of child bearing potential only
- 4. Or earlier when there is evidence of remission or progression in the peripheral blood
- 5. Research samples should be taken between days 22-25 (or on a Monday Thursday at baseline) so that they can be received by the biobank. Both research samples (bone marrow and blood samples) should be collected on the same day
- 6. For patients continuing trial treatment beyond cycle 6, bone marrow aspirate, trephine and disease assessments are recommended every 3 months and at progression/relapse. Patients will have a final disease assessment when the additional treatment stops using the information of the most recent previous bone marrow obtained
- 7. The haematology and biochemistry assessments can be performed between days 22-25 to coincide with the collection of research blood and bone marrow samples or safety bloods
- 8. Dose modifications permitted in accordance with section 7.8 of the protocol after cycle 1
- 9. Administered at Chief Investigator's discretion following 6 cycles of combination treatment if patient obtaining clinical benefit
- 10. Patients will be followed up for a minimum of 12 months from study entry for survival and outcome data

# 7.4 Assessment Schedule – Observational Component

Study schedule 	At registration	End of Month 3	End of Month 6	End of Month 12			
Informed consent	x						
Medical History & Demographics	x						
Information of further treatment		x	x	x			
Collection of routine full blood count results	x	x	x	x			
Collection of routine peripheral blood smear results (blast assessment)	Results to be collec	Results to be collected if assessment performed as part of routine clinical practice					
Disease Assessment		x	x	x			
Quality of Life Assessment (optional)	x	x	x				
Blood Samples for Biobanking (optional)	x	x	x				
Bone marrow for Biobanking (optional)	Sample to be collected in						
Nail clippings and/or saliva collection for germline DNA (optional)	x						

1. Efforts should be made to perform assessments during patient's routine visits rather than asking the patients to attend clinic for extra visits. Assessments should be performed as closely as possible to the schedule outlined above.

# 7.5 Assessments – Interventional Component

#### 7.5.1 Medical History and Demographics

A medical history and the patient's demographics will be taken within 28 days of registration including the following:

- Age
- Sex
- Disease type (current and prior)
- Disease status

- Previous medical conditions
- Previous treatments
- Cytogenetic status

# 7.5.2 Physical examination/symptom assessment

A physical examination and symptom assessment will be assessed within 7 days prior to registration, within 7 days of the start of each cycle of treatment and following treatment discontinuation and will include:

- ECOG performance status
- Blood pressure
- Pulse
- Height (baseline only)

- Weight
- BSA (prior to prescription)
- Transfusion assessment
- Palpation of spleen and liver

# 7.5.3 ECGs

ECG's will be conducted within 7 days prior to registration, weekly during the first cycle and as clinically indicated in subsequent cycles. ECG's should be considered more frequently for patients with a history of significant cardiovascular disease or patients taking medicines which are associated with significant QT prolongation or anti-arrhythmic medications.

#### 7.5.4 Pregnancy testing and contraception

A pregnancy test (serum/urine) for females of child bearing potential must be performed within 7 days prior to registration.

Females of childbearing potential: Must have a negative pregnancy test and should not be breastfeeding. Females must agree to use a reliable form of contraception during the trial and for at least three months after treatment has finished.

Males (whose partner may become pregnant): Must agree to use a reliable form of contraception or during the trial and for three months after treatment has finished.

#### 7.5.5 Haematology

A full blood count will be conducted within 7 days prior to registration, weekly in the first cycle, on day 1, 8 and 22 of cycles 2-6 and at the end of study visit. If the patient continues treatment beyond cycle 6, a full blood count will be performed on day 1 and 22 of all subsequent cycles. Day 22 assessment can be performed during days 22-25 to coincide with the collection of research blood and bone marrow samples or safety bloods.

Full blood counts include:

- Red blood cells
- Haemoglobin
- White blood cells

- Haematocrit
- Absolute neutrophil count
- Lymphocytes

Platelets

In the event of permanent azacitidine discontinuation occurring after completion of the first cycle of treatment, haematology assessments will only be required on a monthly basis as a minimum at the investigator's discretion. These assessments should be performed on Day 1 of each month. Frequent monitoring of haematology parameters is still required when ruxolitinib is co-administered with strong

ALP

eGFR

ALT/AST

CYP3A4 inhibitors, dual inhibitors of CYP2C9 and CYP3A4 enzymes; refer to section 7.11 for further information.

A peripheral blood smear including percentage blasts should be performed in the first instance during screening (within 28 days prior to registration) to assess whether patient is expected to fulfil the bone marrow blasts eligibility criterion and its result reported to the Trial Office in order to confirm the booked treatment slot. Additional peripheral blood smears should be done once per cycle between day 22 and day 1 of the next cycle.

# 7.5.6 Blood chemistry

Biochemistry tests will be conducted within 7 days prior to registration, weekly in the first cycle, on day 1, 8 and 22 of cycles 2-6 and at the end of study visit. If the patient continues treatment beyond cycle 6, biochemistry tests will be performed on day 1 and 22 of all subsequent cycles. Day 22 assessment can be performed during days 22-25 to coincide with the collection of research blood and bone marrow samples or safety bloods.

Biochemistry tests will include\*:

Sodium

Creatinine

Total Protein

- PotassiumMagnesium
- Albumin

Calcium

• Bilirubin

Urea

LDH‡

\*Biochemistry to include bicarbonate if clinically indicated (see section 7.8).

•

‡Treatment with Ruxolitinib has been associated with increases in lipid parameters including total cholesterol, high-density lipoprotein (HDL) cholesterol, low-density lipoprotein (LDL) cholesterol, and triglycerides. Lipid monitoring and treatment of dyslipidaemia according to current clinical guidelines is therefore recommended.

# 7.5.7 Bone Marrow

A bone marrow aspirate and trephine must be conducted within 28 days prior to registration to assess patient eligibility (blasts  $\geq$ 10%), stratify the patient into MPN-AP or MPN-BP and determine the response assessment criteria to be used during the trial. The baseline bone marrow assessments recorded on the Baseline Form should be consistent with the stratification reported on the Eligibility Form.

A further bone marrow should be performed during days 22-25 of cycle 3 and cycle 6 or sooner if there is evidence of remission or progression in the peripheral blood. If the patient continues treatment beyond cycle 6, a bone marrow aspirate and trephine should be performed 3-monthly at the investigators discretion and at the time of relapse/progression. Morphological, immunophenotypic and cytogenetic characterisation and assessment of fibrosis, according to the WHO grading [14], should be performed locally using these samples to determine response to therapy.

# 7.5.8 Disease Assessment

Patients will have their disease assessed at the end of cycle 3 and 6. If patients continue treatment beyond 6 cycles, disease assessment is recommended every 3 cycles. Patients will have a final disease assessment when the additional treatment stops using the information of the most recent previous bone marrow obtained. During these disease assessments, patients will be evaluated for response using the following criteria:

- Patients with ≥20% bone marrow blasts at baseline will be analysed using the "proposed criteria for response assessment in patients treated in clinical trials for MPNs in blast phase (MPN-BP): Formal recommendations from the post-MPN acute myeloid leukaemia consortium"[1]
- **Patients with <20% bone marrow blasts at baseline** will be analysed using the IWG response criteria for MDS patients [2]

Both criteria can be found in Appendix 1.

# 7.5.9 Transfusion Assessment

All transfusions (red blood cells and platelets) that the patient receives from 8 weeks prior to registration until the end of the study should be recorded at every visit.

### 7.5.10 Quality of Life Assessment

All patients in PHAZAR will be asked to complete QoL questionnaires.

The EORTC QLQ-C30, EQ-5D and Myeloproliferative Neoplasm Self-Assessment Form (MPN-SAF) questionnaires (see Appendix 6) will be used to assess QoL and health outcome on Day 1 of cycle 1, cycle 2, cycle 4 and cycle 6 (before dosing).

- The QLQ-C30 is composed of both multi-item scales and single-item measures. These include five functional scales (physical, role, emotional, cognitive and social), three symptom scales (fatigue, pain, and nausea and vomiting) a global health status/QoL scale, and six single items.
- The EQ-5D is a standardised instrument for use as a measure of health outcome. The EQ-5D-5L descriptive system comprises of five dimensions (mobility, self-care, usual activities, pain/discomfort, anxiety/depression).
- The MPN-SAF was created to function as a single instrument of patient-reported symptoms for the entire spectrum of patients with MPN. It is comprehensive and reliable and concisely assesses the prevalence and severity of symptoms of MF, PV, and ET, not captured in other instruments.

The three questionnaires are to be administered at the clinic under the supervision of study staff.

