# SCHEDULE OF ASSESSMENTS – INTERVENTIONAL COMPONENT

	Base	eline		Сус	le 1		С	ycle	2		Cycle	93	c	ycle	4	c	ycle	5		Cycl	e 6	Subse	equent cles	End of Study 
Study schedule 	Within 28 days of registration	Within 7 days of registration	1	8	15	22	1	8	22	1	8	22	1	8	22	1	8	22	1	8	22	1	22	28 days after last treatment
Informed consent	х																							
Medical history & demographics	x																							
Physical examination and vital signs		x				x 			x 			x 			x 			x 			x²		x 	x
ECG		х	x	x	x	x x << as clinically indicated >>																		
Pregnancy test 		х																						
Haematology and biochemistry		x	x	x	x	x 	x	x	x 	х	x	x 	х	x	x 	x	x	x 	x	x	x 	х	x 	x
Peripheral blood smear (blast assessment)	x					x 			x 			x 			x 			x 			x 		x 	
Bone marrow inc. cytogenetics	x 											x 									x 		x 	
Disease assessment												x									x		x 	
Bone marrow for biobanking	x 											x 									x 			
Blood Samples for biobanking	x 											x 									x 			
Nail clippings and/or saliva collection for germline DNA	x																							
Transfusion assessment		x		Throughout Study																				

	Base	eline		Сус	le 1		С	ycle :	2		Cycle	93	С	ycle	4	c	Sycle	5		Cycl	e 6	Subse	equent cles	End of Study 
Study schedule 	Within 28 days of registration	Within 7 days of registration	1	8	15	22	1	8	22	1	8	22	1	8	22	1	8	22	1	8	22	1	22	28 days after last treatment
Quality of life assessment			x				x						x						х					
Adverse event reporting										-		Th	ough	nout	study	,			-					x
Concomitant medication		x		Throughout study																				
Ruxolitinib				Daily   Daily throughout study  x 																				
5-Azacitidine				6 cycles in 5-2-2 schedule x 																				

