#### Secondary

- Best response following 3 and 6 cycles of treatment
  - Assessment will be made according to the following criteria:
    - "Proposed criteria for response assessment in patients treated in clinical trials for MPNs in blast phase (MPN-BP): Formal recommendations from the post-MPN acute myeloid leukaemia consortium" (for patients with ≥20% bone marrow blasts at baseline)[1]
    - International Working Group (IWG) response criteria in myelodysplasia (for patients with <20% bone marrow blasts at baseline)[2]

- Change in the proportion of patients who require transfusion of red cells or platelets after completion of cycles 3 and 6
- Achievement of red blood cell (RBC) transfusion independence after completion of cycles 3 and 6.
- Achievement of platelet transfusion independence after completion of cycles 3 and 6.
- Change in palpable splenomegaly or hepatomegaly after completion of cycles 3 and 6.
- Duration of Complete Response (CR) or Partial Response (PR)
- 12 months Progression-free survival (PFS)
- 12 months Leukaemia-free survival (LFS)

- 12 months Overall survival (OS)
- Duration of trial treatment
- Clinical improvement in haemoglobin level
- Clinical improvement in platelet count
- Quality of life as measured by the MPN SAF; EQ-5D-5L and EORTC QLQ-C30 (baseline and cycles 1, 2, 4 and 6)

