# 7.12 Patient Follow Up

#### Interventional Component

Patients who are gaining clinical benefit at the end of 6 cycles may continue to receive therapy with 5azacitidine and/or ruxolitinib at the discretion of the CI until loss of response or unacceptable toxicity. Patients that have to discontinue the combination therapy due to a toxicity that is clearly related to just one of the trial treatments may continue to take the alternative medication as long as they continue to obtain a clinical benefit in the view of the local investigator and the Chief Investigator (section 7.8.1). Patients will be followed-up for survival data for a minimum of 1 year from the date of start of treatment.

All patients must have a final assessment 28 days after the last dose of trial medication.

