# 7.13 Treatment Discontinuation and Patient Withdrawal

In the event of discontinuation of study treatment, e.g. unacceptable toxicity or patient choice, full details of the reason/s for discontinuation should be recorded on the CRF.

All patients, including non-compliant subjects, should be followed up according to the protocol unless they withdraw specific consent.

In the event of a patient's decision to withdraw from the trial, the Investigator should ascertain from which aspects of the trial the patient wishes to withdraw and record the details on the appropriate CRF. All information and blood/tissue samples collected up until the point of retraction will be retained and analysed. If a patient chooses to withdraw from treatment only (interventional arm only), the patient should discontinue treatment and continue to be assessed in accordance with the protocol. If a patient wishes to withdraw from the trial (i.e. including trial specific assessments), but is willing for further data to be supplied to the Trials Office, then further routine 'follow-up' data (e.g. toxicity data) will continue to be supplied by the Investigator to the Trials Office.

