- Quality of life as measured by the MPN SAF; EQ-5D-5L and EORTC QLQ-C30 (at beginning of cycles 1, 2, 4 and 6)

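### Interventional quality of life is scheduled only at the start of cycles 1, 2, 4 and 6 and not at the compulsory End of Study visit, so patients who stop both drugs early have no further scheduled questionnaire

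*Protocol*

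**What the plan says.** Protocol section 7.5.10 states that the EORTC QLQ-C30, EQ-5D and MPN-SAF "will be used to assess QoL and health outcome on Day 1 of cycle 1, cycle 2, cycle 4 and cycle 6 (before dosing". Section 12.2.1.2 lists the same outcome as measured "at beginning of cycles 1, 2, 4 and 6". Section 2.2 words it as "baseline and cycles 1, 2, 4 and 6", but neither copy of the schedule (the one at the front and the one in section 7.3) has a quality-of-life assessment before cycle 1 Day 1.

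In both copies the quality-of-life row is marked in four columns only. The End of Study column, headed "28 days after last treatment", is marked for physical examination, haematology and biochemistry, and adverse events, but is blank for quality of life. Section 7.12 makes that visit compulsory: "All patients must have a final assessment 28 days after the last dose of trial medication".

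On patients who stop, section 7.13 says: "All patients, including non-compliant subjects, should be followed up according to the protocol unless they withdraw specific consent". For withdrawal from treatment only, it says that "the patient should discontinue treatment and continue to be assessed in accordance with the protocol".

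The observational component is set up differently. Section 7.6.4 asks at registration and after 3 and 6 months, whatever the treatment. Section 12.3 says only that quality-of-life data will be reported descriptively.

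**The concern.** The questionnaires depend on a treatment cycle starting. A patient with no further cycle has no Day 1 and no dose to precede, so nothing further is due. Early stopping is part of this design: section 7.8.1 requires the drug related to a cycle 1 DLT to be discontinued, and both drugs if the event cannot be attributed to one of them. Section 7.8.2 adds discontinuation after long or repeated cycle delays.

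Two things are at stake. First, the patients whose quality of life is most affected by toxicity or progression may contribute only a cycle 1 Day 1 score, so the outcome says least about those in whom tolerability was worst. Second, scores at cycles 4 and 6 describe a group selected by having stayed on treatment.

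There is also a gap at the end of planned treatment. Response is assessed at the end of cycle 6, but the last questionnaire is on Day 1 of that cycle, after five completed cycles.

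**Working it through.** The protocol gives no figure on quality-of-life completeness, so there is none to reproduce. The check has four steps.

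**1. Scheduled time points.** The quality-of-life row set against the 24 visit columns of the schedule:

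| Visit | Questionnaire scheduled |
|---|---|
| Cycle 1 Day 1 | yes |
| Cycle 2 Day 1 | yes |
| Cycle 4 Day 1 | yes |
| Cycle 6 Day 1 | yes |
| After completion of cycle 6, subsequent cycles | no |
| End of Study, 28 days after last treatment | no |

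**2. Does section 7.13 fill the gap?** It tells sites to go on assessing according to the protocol. For quality of life, the protocol offers only pre-dose cycle days. For a patient off both drugs, the instruction points to a time that never comes. Off-treatment quality of life is left unresolved; it is not expressly excluded.

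**3. How many patients could be affected?** The protocol gives no drop-out rate, so these figures only indicate scale.
- Cycle 1 DLT: at the 25% target rate, 0.25 × 34 = 8.5 patients. The number would be lower at doses below the MTD, and some of these patients may continue the unrelated drug.
- Death: assume exponential survival, S(d) = exp(−ln 2 × d / median), with no cycle delays. Section 1.1 cites a 6-month median from one study of intensive induction in blast phase; 12 months is an assumed alternative.

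| Median (days) | Day 28 (C2D1) | Day 84 (C4D1) | Day 140 (C6D1) |
|---|---|---|---|
| 6 months (182.6) | 0.899 × 34 = 30.6 | 0.727 × 34 = 24.7 | 0.588 × 34 = 20.0 |
| 12 months (365.25) | 0.948 × 34 = 32.2 | 0.853 × 34 = 29.0 | 0.767 × 34 = 26.1 |

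These are losses to death, which no extra questionnaire can recover. The avoidable loss is among patients alive but off treatment, and the protocol gives nothing from which to estimate it.

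**4. How far could selection move a mean?** Take a standard normal score with no true change, correlated ρ with a normal propensity to stay on treatment. If a fraction r is retained, the mean among those retained shifts by ρ × φ(z₁₋ᵣ) / r SD. For r = 0.6: z₀.₄ = −0.253, φ = 0.386, and 0.386 / 0.6 = 0.644.

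| Retained | ρ = −0.3 | ρ = 0 | ρ = 0.3 | ρ = 0.6 |
|---|---|---|---|---|
| 80% | −0.10 | 0 | +0.10 | +0.21 |
| 60% | −0.19 | 0 | +0.19 | +0.39 |
| 40% | −0.29 | 0 | +0.29 | +0.58 |

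Positive values mean that the retained group looks better. All values of r and ρ are assumed. The shift applies to a mean per visit. If no patient's score changes, the within-patient change is zero, but that summary too describes only those who stayed.

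**The case against.** The strongest reply is that this is one of many descriptive secondary outcomes in a phase Ib trial whose primary outcome is the MTD. No test is planned and no comparison is made with the observational component. Section 12.3 does not commit to raw means per cycle, and paired change, denominators and missing-data handling commonly belong in the SAP. All of this stands, so the choice of summary is no fault in the protocol. It does not answer the point about collection: the protocol schedule decides whether a questionnaire is given, and no SAP method recovers scores that were never requested.

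A reader might infer that later scores come only from patients still on treatment. That goes too far. Section 7.13 keeps patients who stop under protocol assessment, and patients who stop one drug may continue the other.

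A reader might also infer that the trend will improve through drop-out. The documents do not support that either. Worse patients stopping earlier is plausible, but if stopping is unrelated to quality of life the shift is zero, and with a negative correlation it reverses. Nor can the 6-month median be taken as this trial's prognosis: the trial also enrols accelerated-phase patients with 10-19% blasts and gives a different treatment.

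Finally, an End of Study score is not comparable in timing with cycle 4 or 6. It falls at a different time for each patient and may come long after cycle 6 in those who continue. That is a real limit of the remedy, and it is why calendar-time collection is offered as an option.

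**Conclusion.** The point holds as a gap in collection. Interventional quality of life is tied to four pre-dose cycle days and omitted from a compulsory visit. As a result, patients who stop both drugs early have no further scheduled questionnaire, and no score follows completion of cycle 6. The general rule in section 7.13 does not close the gap, because no listed time point applies to these patients.

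The cycle 4 and 6 summaries are therefore open to selection. They may look better than the whole group if patients with worse quality of life stop earlier. The size and sign cannot be derived from the protocol. The range of 0 to about 0.39 SD at 60% retained rests on an assumed correlation of 0 to 0.6, an assumed retention and a normal model. The MTD and its analysis are unaffected. This is a cheap improvement worth making, and it does not threaten the trial's main conclusion.

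**What to change.** Add the three questionnaires to the End of Study visit in section 7.5.10 and in the quality-of-life row of both copies of the schedule. List that time point in sections 2.2 and 12.2.1.2, with the synopsis brought into line. In the same edit, settle whether the separate baseline named in section 2.2 means cycle 1 Day 1.

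Optionally, also collect the questionnaires at months 3 and 6 regardless of treatment, as the observational component does. Six cycles without delay end at 6 × 28 = 168 days and six months is about 182.6 days, so in a patient treated on schedule the month 6 score would also follow completion of cycle 6.

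Report the number completing out of the number alive at each time point. The choice between paired change and means may be left to the SAP.

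The basic change costs one more questionnaire set per patient at a visit that already takes place. Some patients will be too ill to complete it, and its timing will differ between patients, so it should be summarised separately from the cycle-based scores. The optional months 3 and 6 would add further questionnaire sets, including for patients no longer attending for treatment.
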